| 8.0 SHARING OF RESULTS WITH SUBJECTS | 7.3 Describe the procedures to release data or specimens, including: (the process to request a data/specimen release, approvals required for release, who can obtain data or specimens, and the data to be provided with the specimens. |
| | Data will only be available to members of the study research team. |
| 9.0 STUDY TIMELINES | 8.1 Describe whether results (study results or individual subject results, such as results of investigational diagnostic tests, genetic tests, or incidental findings) will be shared with subjects or others (e.g., the subject's primary care physician) and if so, describe the process for sharing. If you do not intend to share any results, please state that here. |
| | Results will not be shared with participants or any of their medical providers. |
| 9.0 STUDY TIMELINES | 9.1 Describe the duration of an individual subject's participation in the study. List the number of study visits or frequency of study visits. |
| | For Aim 1, participants who participate in the GLA only will be in the study for 1 visit on one day. If participants choose to participate in the optional Action Planning session, they will do 2-3 visits over the course of approximately 2 months. |
| | For Aim 2, individual subjects will be in the study for approximately 8 months. Depending on randomization, participants will either complete 2-3 total visits at the beginning and end of the 8-month timeline or complete 8 monthly visits. |
| | 9.2 Describe the timeline allotted for the enrollment of subjects. |
| | Subjects will be enrolled during the first year of grant funding. |
| | 9.3 Describe the estimated date for the investigators to complete this study (complete primary analysis). |
| | Data collection for this study will span 24 months, with the projected start date of January 2021. Primary analysis will be completed within a year of the last data collected for the current project. |

TEMPLATE: RESEARCH PROTOCOL

NUMBER

HRP-503

ACTIVE DATE

02-04-2020

PAGE

16 of 44

| | | | |
|--|---|--|--|
| 
10.0 INCLUSION AND EXCLUSION CRITERIA & VULNERABLE POPULATIONS
 | 
10.1 Describe how subjects will be screened for eligibility.
 
For Aim 2, participants will be screened for eligibility via phone call from study staff prior to their baseline visit.
 
10.2 Describe/list the inclusion/exclusion criteria for the study.
 
Inclusion criteria for the GLA methodology are that the person is involved in the Every Child Succeeds home visiting program. This involvement will include a number of different roles such as board member, community partner, mother receiving service, former participant in the program, etc. Participants must also be either English or Spanish speaking.
 
Inclusion criteria for the intervention methodology are: 1) child age 2 months at the time of the baseline study visit, 2) English or Spanish speaking, 3) maternal age is equal to or over 18 years, 4) singleton, and 5) no major congenital anomalies or medical conditions requiring specialized feeding.
 | | |
| | 
10.3 Indicate specifically whether you will include each of the following vulnerable populations. Check all that apply. (You may not include members of the below populations as subjects in your research unless you indicate this in your inclusion criteria and are approved by the IRB to include them in your research) The member checklists are for reference only to ensure you provide appropriate safeguards and justification. The checklists do not need to be completed.
 | | |
| |  Adults unable to consent (cognitively impaired individuals) (HRP-417 – MEMBER CHECKLIST Cognitively Impaired) | | |
| |  Individuals who are not yet adults (infants, children, teenagers) (HRP-416 – MEMBER CHECKLIST Children) |  Individuals who are not yet adults and are, or may become, wards of the state. | |
| |  Pregnant women (a woman shall be assumed pregnant if she exhibits and of the presumptive signs of pregnancy, such as a missed menses, until the results of a pregnancy test are negative or until delivery.) (HRP-412 MEMBER CHECKLIST Pregnant Women) | | |
| |  Non-Viable Neonates (HRP-413 – MEMBER CHECKLIST Non-Viable Neonates) | | |
| |  Uncertain Viability Neonates (HRP-414 – MEMBER CHECKLIST Uncertain Viability Neonates) | | |
| |  Prisoners (HRP-415 – MEMBER CHECKLIST Prisoners) | | |
| | 
10.4 If the research involves individuals listed in 10.3 or other individuals who are vulnerable to coercion or undue influence, please justify based on
 | | |

TEMPLATE: RESEARCH PROTOCOL

| NUMBER | ACTIVE DATE | PAGE |
|---------|-------------|----------|
| HRP-503 | 02-04-2020 | 17 of 44 |

| | |
|--|---|
| | 
the applicable checklist and describe additional safeguards included to protect their rights and welfare.
 |
| | 
Participants in the pilot testing of the HEMI program will be infants enrolled at 2 months of age and their mothers. Our obesity prevention program specifically targets healthy eating between 3-8 months of age making it necessary for our study to include infants as the targeted population. All study staff have experience working with child populations, and the investigative team has significant experience in clinical care and research with children. Cincinnati Children's Hospital Medical Center is a facility 100% devoted to research and treatment of children, and PI [name] lab (i.e., the Healthy Kids Lab) was established specifically for research regarding children's health.
 |
| | 
The Every Child Succeeds home visiting program provides services to families who are pregnant or with young children. Therefore, some Every Child Succeeds families who participate in the GLA phase may be pregnant women.
 |
| | 
10.5 If the research involves or may involve individuals who are students or employees where the research is taking place, please describe additional safeguards included to protect their rights and welfare.
 |
| | 
Not Applicable
 |
| 
11.0 NUMBER OF SUBJECTS
 | 
11.1 Indicate the total number of subjects to be accrued.
 |
| | 
For Aim 1, there will be no more than 100 participants.
 
For Aim 2, we will recruit 30 infants and their mothers.
 
11.2 If applicable, distinguish between the number of subjects who are expected to be enrolled and screened, and the number of subjects needed to complete the research procedures.
 
Approximately 15 women enroll in the ECS program each week (~800 per year), providing a large sample pool from which to enroll participants. We anticipate that 50% (n=400) of eligible ECS mother-child dyads will be referred to the study (~7-8 per week). Participants will receive their enrollment visit when the child is 2-months of age. Informed by retention data from the ECS program, 85% (n=340) of the participants will remain active in the program when child is 2-months of age (criterion for eligibility). We anticipate 60% will agree to participate in the study (~4 per week).
 |
| 
12.0 RECRUITMENT METHODS
 | 
12.1 Describe when, where, and how potential subjects will be recruited.
 
GLA Phase: Leadership, board members, community partners, and home visitors will be invited for involvement in the GLA through personal correspondence and advertising through standard ECS communications and meetings. Participating families will be informed about the study by ECS home visitors. Word-of-mouth and snowballing (i.e., one participant informing others who might be interested in the
 |

TEMPLATE: RESEARCH PROTOCOL

| NUMBER | ACTIVE DATE | PAGE |
|---------|-------------|----------|
| HRP-503 | 02-04-2020 | 18 of 44 |

assessment) will also be largely utilized. Prior to the start of the GLA session, participants will be provided with the required elements of consent.

Intervention Pilot Testing: Participants will be families participating in the Every Child Succeeds (ECS) home visiting program. These participants will be recruited by ECS home visitors. Home visitors will refer eligible participants to our research coordinators who will contact families via phone to tell them more about the research study. Interested families will complete a screening over the phone with a study research coordinator to assess inclusion criteria. If a child meets inclusion criteria and the family is interested in participating, they will be scheduled for a first study visit. Because of the home visitor time it will take to complete referrals, we need to compensate them for their time. We will be paying home visitors or the agency employing home visitors \$15 per each referral completed. Because this is compensation for their time and is not a finders fee, they receive \$15 per referral even if the family says no and decides to not participate in the study or even if a family is not reached to further discuss the study.

12.2 Describe the source of the subjects.

Participants will be leaders, board members, community partners, home visitors, and families from the Every Child Succeeds (ECS) program. ECS was founded in 1999 and provides home visiting services to sociodemographically at-risk mothers in Southwestern Ohio and northern Kentucky. Mothers are eligible for participation if they meet at least one of 4 demographic factors: unmarried, low income, under the age of 18, and inadequate prenatal care. Administered by CCHMC, ECS has up to 3,000 families enrolled at any given time served by 115 home visitors in nine locally-embedded community agencies.

12.3 Describe the materials that will be used to recruit subjects. (Attach copies of these documents in the Recruitment section on the local site documents page in RAP. For advertisements, attach the final copy of printed advertisements (avoid making copies until approved in case modifications are required). When advertisements are taped for broadcast, attach the final audio/video tape. You may submit the wording of the advertisement prior to taping to preclude re-taping because of inappropriate wording, provided the IRB reviews the final audio/video tape)

For Aim 1, participants will be recruited through emails and word of mouth including use of the Recruitment Flyer uploaded in the RAP system. For Aim 2, recruitment will occur via verbal referral by ECS home visitors and will utilize IRB approved recruitment flyers.

13.1 Describe the amount, method, and timing of payments to subjects.

13.0 COMPENSATION FOR SUBJECTS

For Aim 1 (GLA), participants will earn \$20 in gift cards for participating in each visit. Participants will have the option to be part of 1-3 visits, and so can earn up to a total of \$60.

| | |
|---|---|
| | 
For Aim 2, participants will receive up to \$100 for participating: \$40 after participating in the baseline visit (when the infant is around 2 months of age) and \$60 for completing the post-treatment visit (when the infant is around 9 months of age). We are providing this amount to participants through gift cards. At enrollment, participants will receive lab-branded materials such as a notepad to record study appointments, pen, and tote bag; the total value of these items is less than \$25. When families complete the intervention, they will also receive a token to celebrate their graduation from the program which will be valued at less than \$15 (e.g., a t-shirt for their child with the lab name, a stuffed animal for their child with the lab name on it). s
 |
| 
14.0 WITHDRAWAL OF SUBJECTS
 | 
14.1 Describe the anticipated circumstances under which subjects will be withdrawn by the study team from the research without their consent. Not Applicable
 
14.2 Describe any procedures for orderly termination. Not Applicable
 
14.3 Describe procedures that will be followed when subjects withdraw from the research, including partial withdrawal from procedures with continued data collection, withdrawal of previously collected data upon request, etc. Consent may be withdrawn by the participant at any time during the study. Participants will be made aware of this right during the consent process.
 |
| 
15.0 RISKS TO SUBJECTS
 | 
15.1 Describe the reasonably foreseeable risks, discomforts, hazards, or inconveniences to the subjects related to the subjects' participation in the research. It may be useful to include: a description of the probability, magnitude, duration, and reversibility of the risks. Consider the physical, psychological, social, legal, and economic risks. Potential risks to participants are expected to be relatively low. Participants will be informed of the efforts that will be made to keep their responses confidential, and the limits of confidentiality will also be reviewed. Potential risks of choking or growth faltering will be monitored at each study contact. Also, there is increased risk of COVID-19 exposure at the present time. However, telecommunication could be used for completion of all study visits if necessary per COVID-19 recommendations and protocols at the time of data collection to reduce this risk for participants (see 15.5).
 |
| | 
15.2 If applicable, indicate which procedures may have risks to the subjects that are currently unforeseeable. Not Applicable
 
15.3 If applicable, indicate which procedures may have risks to an embryo or fetus should the subject or the subject's partner be or become pregnant. Not Applicable
 |

| | |
|--|--|
| | 
15.4 If applicable, describe risks to those who are not subjects.
 
Not Applicable
 
15.5 Describe the procedures and actions taken to mitigate the risks to subjects and others.
 
Families will be notified if our independent safety monitor (ISM) identifies any greater risk in the treatment condition, but at this time we do not believe there is any increased risk from our treatment. An ISM external to the study team will be identified to assess any potential changes in the known risks of participating in this study.
 
Our study team will also minimize participant and study staff COVID-19 exposure, transmission, and infection by implementing all COVID-19 related policies and procedures in place at the time of data collection. Telecommunication strategies may be used rather than in-person data collection if warranted based on COVID-19 risk and recommendations. Any in-person activities will only be adopted when the university COVID-19 research guidelines permit these activities to resume. The IRB will be notified via RNI at that time, if indicated by revised guidelines.
 |
| 
16.0 POTENTIAL BENEFITS TO SUBJECTS
 | 
16.1 Describe the potential benefits that individual subjects may experience from taking part in the research. It may be useful to include: the probability, magnitude, and duration of the potential benefits. Indicate if there is no direct benefit to subjects. Do not include benefits to society or to others.
 
Mothers may benefit from participation in the study through receipt of a potentially efficacious intervention to promote healthy infant feeding and reduce subsequent obesity-risk.
 |
| 
17.0 DATA MANAGEMENT AND CONFIDENTIALITY
 | 
17.1 Describe the data analysis plan, including any statistical procedures or power analyses.
 
Aim 1: GLA data analysis will be conducted in real-time by the participants during the session. Participants will reach consensus on overall themes and action items.
 
Aim 2: Proportion of infants with BMI ≥ 85th percentile will be compared between the treatment and control group using a Fisher's exact test of independence, including all randomized participants in an intention to treat framework. If baseline differences are found between groups, these baseline variables will be included in an adjusted logistic regression model with odds ratios of the intervention group estimated relative to the control group. Sensitivity analyses will examine the impact of treatment fidelity on intervention efficacy. Secondary outcomes of infant diet diversity and servings of fruits and vegetables will be evaluated using general linear models, adjusting for baseline characteristics as needed. Infant biological sex and participation in other supplemental nutrition programs (e.g., WIC) will be explored as potential moderators of treatment outcomes.
 
17.2 Describe the steps that will be taken to secure the data.
 |

TEMPLATE: RESEARCH PROTOCOL

| NUMBER | ACTIVE DATE | PAGE |
|---------|-------------|----------|
| HRP-503 | 02-04-2020 | 21 of 44 |

Aim 1: For aim 1, participants will complete demographic information in an online survey. In this survey, they will also need to indicate their email address in order to receive their electronic gift card for participation in the group. They will also be asked on the form their interest in participating in subsequent action planning groups, and we will use their email to contact interested participants. In order to secure confidentiality of demographic data, we will remove the potentially identifying email address from the database as soon as the groups are completed.

Aim 2: Demographic information and maternal quantitative feedback on the intervention will be obtained through an online survey using the data capturing system REDCap. Maternal qualitative feedback on the intervention will be obtained via interview at the post-treatment study visit, and peer counselors will also complete qualitative interviews with research staff to provide feedback on the intervention. All data will be identified with ID numbers only, and the list linking ID numbers to participant names will be kept in a password-protected document separate from all other participant data on a password protected computer and secure server. Only study staff will have access to participant identifiable information during the study.

17.3 Describe any procedures that will be used for quality control of data collection.

Infant anthropometric measurements will be recorded on paper-and-pencil forms, and dietary information will be retrieved via phone interview. All other maternal-report measures will be completed through a REDCap survey on a tablet. REDCap software is administered by the Center for Clinical and Translational Science and Training (CCTST). The REDCap survey and database will be built by study staff, and tested for accuracy until all issues have been resolved prior to moving the survey into production for data collection. Only study staff will have access to the REDCap database.

Each treatment session will be audio recorded to monitor treatment fidelity. Recordings will be coded by study staff who are not providing the intervention for whether each of the treatment components outlined in the treatment module is covered at each session. All data will be labeled with a subject ID only and stored on password protected computers, on secure network drives, or in locked filing cabinets. Consent forms will be stored in a separate locked filing cabinet. The document linking study ID number to participant names will be password protected and stored in a location separate from other study data. Data collected on paper-and-pencil forms will be entered into the study database by study staff. All manually entered data will receive a second-pass review to ensure accurate entry. Data entry date and the person entering data will be documented on each paper-and-pencil form.

Electronic data and files will be stored on a secure internal network drive with user-level access. This network is backed up in accordance with standard UC IT procedures. A secure restricted data drive will be used to share data electronically with study team members at CCHMC.

17.4 Describe how data or specimens will be handled study wide as outlined below.

| | |
|--|--|
| | 
17.5 What information will be included in the data or associated with the specimens?
 
Research materials will be obtained from participants at the baseline and post-treatment study visits and via telephone interviews. This includes demographic information and maternal quantitative feedback on the intervention. Research staff will also complete infant weight and length measurements using a mobile SECA baby scale and infant length board. Dietary information will be obtained via telephone interviews with trained staff from the Schubert Research Clinic Bionutrition Core.
 
17.6 Who will have access to the data or specimens?
 
Only study staff will have access to participant identifiable information during the study.
 
17.7 Where and how data or specimens will be stored?
 
Electronic data will be stored on a secure internal network drive with user-level access. This network is backed up in accordance with standard University of Cincinnati IT procedures. A secure restricted data drive will be used to share data electronically with the study team members at CCHMC.
 
17.8 How long the data or specimens will be stored?
 
We will retain identifiable information for 2 years after this research ends, to permit longer-term follow up. After that point, all identifying data will be destroyed, and only deidentified study data will be retained for future analyses.
 
17.9 If applicable, how data or specimens will be transported?
 
Not Applicable
 
17.10 Who is responsible for receipt or transmission of the data or specimens?
 
Data will be received or transmitted through a secure network drive or connection. The PI will be responsible for data receipt and transmission.
 |
| 
18.0 PROVISIONS TO MONITOR THE DATA TO ENSURE THE SAFETY OF SUBJECTS
 | 
18.1 For more than minimal risk research, describe the plan to periodically evaluate the data collected regarding both harms and benefits to determine whether the subjects remain safe.
 
Not Applicable. Although the study is considered only minimal risk research, an independent safety monitor (ISM) will be identified during the study start-up phase and whose primary purpose will be to provide guidance regarding adverse events and safety issues. Information regarding the data safety monitoring plan (DSMP) is presented below, even though the study is considered minimal risk.
 
18.2 What data are reviewed, including safety data, untoward events, and efficacy data?
 
The ISM will review relevant participant safety data and make recommendations regarding continuation, modification, or termination of the trial due to safety risk.
 |

TEMPLATE: RESEARCH PROTOCOL

| NUMBER | ACTIVE DATE | PAGE |
|---------|-------------|----------|
| HRP-503 | 02-04-2020 | 23 of 44 |

Communication with the ISM will occur on an as-needed basis when safety concerns arise as well as annual meetings with the study PI to discuss overall trial safety data.

18.3 How will the safety information will be collected?

Adverse event data collection sheets have been established for recording adverse events reported by participants. These forms will be completed at each treatment session (i.e., Session 1, Session 2, Session 4, Session 5, and Post-Treatment) or study visit conducted by a research staff interventionist (i.e., not done at peer counselor-led sessions). For choking episodes, the date of the episode, details of the episode (e.g., food being eaten, situation in which eating occurred), and any intervention required (e.g., medical attention) will be recorded. For growth faltering, caregivers will be asked to describe their concerns regarding their child's growth. Additionally, infant weight will be recorded at each study visit and treatment session (i.e., Session 1, Session 2, Session 4, Session 5, and Post-Treatment) conducted by a research staff interventionist (i.e., not done at peer counselor-led sessions). All other potential adverse events reported to study staff will also be documented.

18.4 The frequency or periodicity of review of cumulative data.

Regularly scheduled meetings between the ISM and PI will occur annually. Emergency meetings will be scheduled by the PI if immediate concerns arise between regularly scheduled meetings.

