The following potential adverse events will be assessed throughout the study period: occurrence of choking episodes during infant feedings (at each study visit and interventionist-led treatment session), growth faltering (monitored at each interventionist-led treatment session for infants in the treatment condition; length and weight will be monitored for all participants [i.e., treatment and control] at baseline and post-treatment), and unexpected adverse events.

Study participants will be informed of any changes to the known risks and benefits of participating in the current study, including if it is identified that treatment participants are at greater risk for adverse events. If participants in the treatment arm experience greater adverse events, possible discontinuation of the study or modification of the intervention will be considered under the guidance of the ISM.

6.5 Where applicable, list and describe the data collection tools such as surveys, data collection forms, etc. All tools described should be uploaded in the RAP Smart Form on the Local Site Documents page unless they are standardized, validated tools.

Demographics Form. Participants in both the intervention and GLA methodologies will complete a demographics form. There is a separate demographic form for each of these methodologies because the interventionist participants will be asked additional demographic details about their participating child, while GLA participants will only report their own adult demographics.

Maternal Feedback on Intervention: Maternal Feedback on the Intervention will be obtained through a quantitative survey and a qualitative interview. The quantitative survey consists of Likert scale ratings on whether they perceived the intervention as suitable, occurring at the right time, being presented clearly, and helpful; mothers will also rate satisfaction with the intervention and their confidence in implementing the recommendations made by the study team. Qualitative interviews will be conducted with each family by a research staff member who was not the study interventionist (to prevent potential bias) to obtain feedback regarding additional information that would be helpful to add to the program, content that was not helpful and could be eliminated from the program, other changes they would like to see to the program, and aspects they would like to see stay the same about the program.

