**NCT04977947**

**03/15/2020**

## Statistical Analyses and Power

### **1. Outcome assessment and definitions**

Our primary outcome for this study is infant Body Mass Index (BMI).

Outcome	Assessed when?	Metric(s)	Continuous or categorical	Maximal range	Hypothesized results
Infant anthropometry	Baseline, post-treatment	Percent of infants with BMI $\geq 85^{\text{th}}$ percentile, by treatment group	Categorical	0% to +100%	Intervention < Control
Infant anthropometry	Baseline, post-treatment	Pre- to post-study change in BMI percentile, by treatment group	Continuous	-99% to +99%	Intervention < Control

Our secondary outcomes are infant diet and intervention acceptability

Outcome	Assessed when?	Metric(s)	Continuous or categorical	Maximal range	Hypothesized results
Infant diet diversity	Baseline, post-treatment	Pre- to post-study change in number of food groups provided in previous day, by treatment group	Continuous	-7 to 7	Intervention > Control
Infant diet quality	Baseline, post-treatment	% kcal from fat  Servings vegetables+ fruits	Continuous	0 or greater	Intervention < Control  Intervention > Control
Treatment adherence	Throughout treatment	Proportion of treatment sessions completed by participants in the treatment condition	Continuous	0 to 6	At least 5 of 6 sessions completed
Treatment fidelity	25% of intervention visits	Provision of intervention components as specified in module	Continuous	Varies relative to module goals	<5% of module components not covered
Maternal feedback	Post-treatment	Proportion of mothers indicating positive view of program	Categorical	0% to 100%	>90% indicate positive view
Peer Counselor feedback	Post-treatment	Qualitative coding of themes	Qualitative	n/a	n/a

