### **3. Statistical Power, Aim 2**

Primary outcomes: Data from a previous study in the *ECS* population identified that 31% of infants had  $\text{BMI} \geq 85^{\text{th}}$  percentile at age 9 months. Assuming this represents the *ECS* control population for this pilot study, 15 infants per group would provide 42% power to detect the reduction of this rate to 0% by 9 months in the intervention group, at  $p < 0.05$ . A similar power (43%) was obtained when modeling continuous change in  $\text{BMI}$  percentile between 3 and 9 months of age, which had a mean (SD) change of 19.6 (29.3) percentile points, assuming the intervention group would achieve no mean change in  $\text{BMI}$  percentile and equal variance with the control group. Thus, this study will be underpowered to identify significant changes due to the intervention, but will enable estimation of the effect size to power larger studies.

Secondary outcomes: Previous observational data from a cohort of Cincinnati infants living in an urban environment found that the number of food groups fed increased by an average of  $3.4 \pm 1.4$  food groups between ages 3-9 months. (Woo 2015) Assuming equal variance between the intervention and control groups, and 15 infants per group, this pilot study would have 75% power to detect a 1 SD (1.4 food group) difference in the increase of food groups between intervention groups at  $p < 0.05$ . We thus anticipate that this pilot intervention will also be underpowered to evaluate changes in our secondary outcomes of infant diet, but will be informative with regard to the anticipated effect size and resulting sample size required in a larger trial.

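### The planned analysis does not show whether a lower BMI-percentile change under HEMI means prevented excess gain or infants moving into the low tail, although the measurements that would show it are taken in both arms

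*Protocol*

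**What the plan says.** **Efficacy.** SAP section 1 lists two metrics under the primary outcome, infant BMI. One is the percentage of infants at or above the 85th percentile. The other is "Pre- to post-study change in BMI percentile, by treatment group", with a range of -99 to +99. The hypothesised result for both is "Intervention < Control". The SAP sets no floor, does not restrict by starting percentile and has no low-percentile outcome. Protocol 17.1 carries only the first metric: "Proportion of infants with BMI ≥ 85th percentile will be compared between the treatment and control group using a Fisher's exact test of independence".

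**Harm.** Protocol 6.3 names growth faltering as a potential adverse event, and 15.1 names it as a risk. Section 18.3 says: "For growth faltering, caregivers will be asked to describe their concerns regarding their child's growth". Its next sentence adds a recorded infant weight at study visits and interventionist-led sessions. Protocol 6.3 places session-level monitoring of faltering in the treatment arm only. For everyone, "length and weight will be monitored for all participants [i.e., treatment and control] at baseline and post-treatment". Section 6.5 has weight and length taken in duplicate, with BMI standardised to the WHO 2005 standards.

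**Safety analysis.** Protocol 18.6 plans ANOVAs on the number of adverse events by arm. It does not say whether event types are separated. The SAP has no safety section. Neither document defines growth faltering by measurement or says how a recorded weight becomes an event.

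**The concern.** A programme meant to slow weight gain has one obvious harm: slowing it too much, or in the wrong infants. That harm moves the continuous primary metric the same way as success does. An infant going from the 50th to the 2nd percentile contributes -48 in the favourable direction. An infant held at the 50th, who would otherwise have risen by the SAP's average of 19.6 points to about the 70th, contributes 0. The metric ranks the first infant as the better result, and the 85th-percentile metric treats the two alike.

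The safety analysis is where the difference ought to appear. It rests on event counts whose faltering entry is a caregiver's description in an unblinded trial, collected on more occasions in one arm than in the other.

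The SAP says the pilot's purpose is to estimate an effect size for larger trials. An estimate that mixes wanted and unwanted falls would carry that ambiguity into the next design.

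**Working it through.** **1. The SAP's own figure.** The inputs come from SAP section 3: "mean (SD) change of 19.6 (29.3) percentile points" in the control population, no mean change under HEMI, equal variance, 15 per arm, p < 0.05 (two-sided assumed). The noncentrality is 19.6 / (29.3 × √(2/15)) = 19.6 / 10.70 = 1.83 on 28 degrees of freedom. Two-sided t-test power is 42.4%, against the stated 43%. The figure reproduces, so the effect the SAP has in mind is an arm mean of 0 against +19.6.

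**2. Different routes to that arm mean.** Route A: every HEMI infant is held 19.6 points below the expected rise. Route B: a fraction f falls by D points and the rest rise 19.6 like controls. Setting -fD + (1 - f) × 19.6 = 0 gives f = 19.6 / (19.6 + D).

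- D = 40: f = 19.6/59.6 = 32.9%, or 4.9 of 15
- D = 50: f = 19.6/69.6 = 28.2%, or 4.2 of 15
- D = 60: f = 19.6/79.6 = 24.6%, or 3.7 of 15

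The values of D are illustrative and are not in the documents. The routes share a mean but not a spread. With SD 29.3 within each group and D = 50, route B has SD √(29.3² + 69.6² × 0.282 × 0.718) = 42.9. The individual data would therefore hint at it, but no planned output looks there.

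**3. What the second metric adds.** If the infants in route B started above the 85th percentile, the proportion at or above the 85th would fall and the change would be visible. If they started near the 50th and ended in the low tail, that proportion would not move because of them. It would not move either if mid-range infants were simply kept from rising to about the 70th. A lower mean with an unchanged proportion therefore leaves open which of these happened.

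**4. What the safety count adds.** Section 18.3 lists forms at Sessions 1, 2, 4 and 5 and at post-treatment, and excludes peer counselor-led sessions. After baseline that makes 4 + 1 = 5 completion points in the HEMI arm and 1 (post-treatment) in the control arm. Unequal detection would tend to raise recorded events under HEMI. The documents do not allow the size of this to be computed. It makes the ANOVA hard to read in either direction.

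**5. What a measured comparison could deliver.** If no infant of 15 met a low-tail criterion, the one-sided 95% upper bound would be 1 - 0.05^(1/15) = 18.1%. By Fisher's exact test, 4 of 15 against 0 of 15 gives p = 0.100, and 5 against 0 gives p = 0.042. Power for assumed rates of 20% v 2% is 12.5%, and for 40% v 2% it is 66.9%. The comparison is descriptive at this size.

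**The case against.** The strongest reply is that the data exist. Weight and length are measured in duplicate in both arms at baseline and post-treatment, and the sentence after the one on caregiver concern records weight. A reader might infer that the trial cannot separate prevented gain from faltering, or that faltering rests on caregiver opinion alone. Neither is supported. What is missing is a prespecified criterion and a planned comparison.

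Second, the 85th-percentile metric does show whether fewer infants are at high BMI. It is the only BMI outcome in the protocol's own analysis plan, and it gives no credit for a fall from the 50th percentile. It would be wrong to say that the trial could not tell whether high BMI became less common. The reply stands that far. It does not reach the lower tail.

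Third, one might quantify the harm by shifting a normal curve. With the SAP's inputs, the share of infants with any fall goes from Φ(-19.6/29.3) = 25% in control to 50% under HEMI. Those figures describe the metric only. They follow from any 19.6-point shift, they include wanted falls from high percentiles, and they come from 3-to-9-month data while the trial measures at 2 and 9 months. No baseline percentile distribution is given, so the number of infants ending in a low tail cannot be derived.

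Fourth, the idea that feeding counselling changes what mothers report as a concern is plausible in an unblinded trial, but no passage supports it, and the point does not need it.

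Finally, the independent safety monitor reviews relevant safety data and meets the investigator annually. That is a safeguard, but 18.2 does not name growth measurements or an arm comparison of them.

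**Conclusion.** The point holds as a gap in the prespecified analysis, not in data collection. As written, a lower mean BMI-percentile change under HEMI could be reported as favourable with no planned output showing where on the percentile scale it arose below the 85th. The planned safety test cannot fill that gap, because its faltering entry has no measured definition and its opportunities for detection differ by arm (5 v 1 after baseline).

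As to size, falls of 40 to 60 points in roughly 4 to 5 of 15 infants would be enough to produce the arm mean that the SAP assumes for success. This shows that the mean is ambiguous; it does not predict that HEMI causes faltering, and nothing in the documents suggests that it does.

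The conclusion assumes that the baseline and 9-month measurements are taken in person, as 6.5 describes. Section 15.1 allows all study visits to be remote if needed, and measured growth would then be incomplete. The calculations also assume a two-sided test and illustrative fall sizes and faltering rates.

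**What to change.** In Protocol 18.3 and 18.6 and in the SAP, add a measured growth safety outcome for both arms:

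- 2-to-9-month change in WHO weight-for-age and BMI z-scores, by arm;
- the number of infants in the low tail at 9 months, by arm and by baseline percentile;
- this table reported beside the primary BMI result and labelled descriptive, with exact confidence limits.

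The independent safety monitor and clinical experts should set the low-tail criterion before anyone sees data by arm. Caregiver concern stays as supplementary information. For event counts, state whether types are separated, and show the events found at the contacts common to both arms apart from those found at treatment sessions.

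Three sets of passages should be reconciled at the same time. Section 15.1 has faltering monitored at every study contact, while 18.3 excludes peer counselor-led sessions. Section 6.5 measures weight and length at in-person treatment visits, while 18.3 names weight only. Section 6.2 allows virtual sessions, at which 18.3 still expects a weight.

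The cost is some wording and one table, with no new measurement. The one drawback is that a favourable mean shift has to be shown together with its lower-tail counterpart, in numbers too small to settle the matter.
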